7.3 Exploratory objectives

- 1. To evaluate the impact of flavors on "product-liking" *vs.* the subjects' usual oral tobacco/nicotine product of choice for all the ZYN Dry products.
- 2. To compare the nicotine extraction-normalized PK parameters AUC_{inf} and C_{max} between the unflavored and flavored ZYN Dry products.

The results of the exploratory objectives may not be reported in the clinical study report (CSR).

7.3.1 Exploratory endpoints

- 1. The difference in "product-liking" *vs.* the subjects' usual oral tobacco/nicotine product of choice between the unflavored and flavored ZYN Dry products, measured on a 3-point scale using a multiple-choice question (MCQ) 60 min after IP administration.
- 2. The difference in nicotine extraction-normalized AUC $_{inf}$ and C_{max} between the unflavored and flavored ZYN Dry products.

CONFIDENTIAL 23 (59)

8 STUDY DESIGN

8.1 Overall study design and schedule of events

This is an open-label, randomized, 9-way cross-over, single dose administration study designed to assess the impact of flavors in OTDN pouches on nicotine exposure. The IPs are OTDN pouches, ZYN Dry 6 mg: including 1 unflavored product (ZYN Dry Smooth) and 8 flavored products (ZYN Dry Virginia Blend, Kentucky Bold, Cherry, Dragonberry, Peach, Wine, Bourbon and Dark Rum).

The study will include 42 randomized subjects with the aim to achieve 36 fully evaluable subjects. The subjects are healthy male or female oral tobacco/nicotine pouch users aged \geq 21 years who have used oral tobacco/nicotine products for \geq 1 year, with a minimum daily consumption of 5 or more pouches. An effort will be made to randomize at least 17 female subjects (~40 %) in the study.

The subjects report to the clinic for a screening visit (Visit 1) followed by 9 treatment visits (Visit 2-10) on separate days. Screening (Visit 1) will take place within 4 weeks prior to Visit 2 and will include an eligibility check, including evaluations of smoking and oral tobacco/nicotine product use, a brief physical examination, laboratory tests, electrocardiograms (ECG) and collection of medical history, vital signs (pulse rate and blood pressure), height, weight, and body mass index (BMI, see Table 8.1-1 for details).

Subjects shall abstain from oral tobacco/nicotine products as well as smoking (cigarettes or e-cigarettes) for at least 12 h prior to each treatment visit (Visit 2-10). To this end, subjects will be instructed to avoid using such products from approximately 20:00 (8 pm) the day before treatment visits. All IP administrations are performed during the morning hours (08:00 to 12:00) to facilitate abstinence. Subjects should certify abstinence before each treatment starts.

The IPs will be administered as single pouches in a pre-determined randomized order. Subjects will keep the pouch still between the upper lip and gum for 60 min and will be instructed not to manipulate the pouch with the tongue or lips. They will also be instructed not to eat or drink, chew gum, or brush their teeth for 30 min before, during, or 30 min after the IP administration [12].

After 60 min each used pouch will be collected and frozen (-20°C) pending analysis of residual nicotine content. Unused pouches from the same batch will serve as references and will be stored at -20 °C pending analyses.

Blood samples for the assessment of nicotine plasma levels and PK parameters will be collected at pre-defined time points from pre-administration to 6 h after each IP administration. The PD effects of the IPs will be determined using pulse rate measurements and subjective parameters (using VAS questions) at the same pre-defined time points as well as an MCQ 60 min after IP administration.

The total duration for each subject in the study will be approximately 5 weeks, not including the preceding 4-week screening period.

See Table 8.1-2 for a detailed schedule of events applicable for each treatment visit.

Study assessments are described in Section 11.

CONFIDENTIAL 24 (59)

Table 8.1-1 Schedule of events

Events	Visit 1 Screening	Visit 2 First treatment visit	Visit 3-10 Treatment visits		
Informed consent	X				
Demographics	X				
Medical/surgical history	X				
History of nicotine use	X				
Inclusion/exclusion criteria	X	X ¹			
Physical examination	X				
Weight and height, BMI	X				
Vital signs (blood pressure and pulse)	X				
Electrocardiogram	X				
HIV, Hepatitis B and C	X				
Pregnancy test ²	X	X ³	X^3		
Urine drug screen ⁴	X	X			
Alcohol screen ⁴	X	X			
Randomization		X			
IP (pouch) administration		X ⁵	X ⁵		
PK blood sampling (plasma)		X ⁵	X ⁵		
Subjective effects (VAS questions and MCQ)		X ⁵	X ⁵		
Pulse rate (pulse oximeter)		X ⁵	X ⁵		
IP (pouch) collection		X ⁵	X ⁵		
Baseline symptoms	X	X			
Adverse events		X	X		
Prior and concomitant medications	X	X	X		

CONFIDENTIAL 25 (59)

¹Confirmation of eligibility criteria.

² Only subjects of child-bearing potential.

³ Only at the discretion of Investigator. Only at the discretion of PI on Visits 2-10.

⁴ Additional drug and alcohol tests may be performed at the discretion of the Investigator during treatment visits.

⁵ The detailed timing of assessments is outlined in Table 8.1-2.

Table 8.1-2 Detailed schedule of events for each treatment visit (Visit 2-10)

	Visit 2 - 10															
ssessment / Time-point	Admission	-00:15	-00:10	-00:01	00:00	50:00	00:10	00:15	00:30	00:45	01:00	01:15	01:30	05:00	04:00	00:90
Inclusion/exclusion criteria	X ¹															
Urine drug screen	X ²															
Alcohol screen	\mathbf{X}^2															
Pregnancy test	X^3															
Randomization	X ⁴															
IP (pouch) administration					X ⁵											
IP (pouch) collection											X ⁵					
PK blood sampling (plasma)			X ^{5, 6}			X ⁵										
VAS question ("craving")			X ⁵			X ⁵	X5	X ⁵								
VAS question ("satisfaction")						X ⁵										
VAS ("product-liking" and "intent-to-use-again")											X ⁵					
MCQ ("product liking" vs. usual product)											X ⁵					
Pulse rate (pulse oximeter)			X ⁵			X ⁵										
Baseline symptoms		X^7											-			
Adverse events								X8					A.			
Prior and concomitant medications	X															

CONFIDENTIAL 26 (59)

¹ Only on Visit 2. Confirmation of eligibility before randomization.
² Only on Visit 2. Additional drug and alcohol tests may be performed during treatment visits at the discretion of the Investigator.

³ Only subjects of child-bearing potential. Only at the discretion of PI on Visits 2-10.

⁴ Randomization occurs only on Visit 2.

⁵ See the timing priority in Section 11.1 and the allowed time deviations in Table 11.1-1.

⁶ Pre-administration PK-sample taken at any time within 15 min prior to IP administration, except in direct association with the pre-administration pulse rate assessment at -10 min.

⁷ Only on Visit 2. Baseline symptoms experienced prior to first IP administration.

⁸ AEs experienced from first IP administration.

8.2 Rationale for study design

This is an open-label, randomized, 9-way cross-over, single dose administration study designed to evaluate the impact of flavors on nicotine uptake from ZYN Dry products.

A cross-over design was chosen to yield a more efficient comparison of treatments (IPs) than a parallel study design, *i.e.*, fewer subjects are required since each subject will serve as its own control. To avoid carryover effects, subjects will abstain from oral tobacco/nicotine products as well as smoking (cigarettes or e-cigarettes) for at least 12 h prior to each treatment visit (Visit 2-10).

Randomization will be used to minimize bias in the assignment of subjects to an IP administration sequence and to increase the likelihood that known and unknown subject attributes (*e.g.*, demographic and baseline characteristics) are evenly balanced.

A copy of the randomization list will be generated and provided to the bioanalytical laboratory and to the pharmacokineticist for their analyses.

CONFIDENTIAL 27 (59)

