9.9 Randomization

On Visit 2, the subjects will be randomized to 1 of 6 IP administration sequences. As this is an open-label study, the IP administration sequence to which each subject is allocated for will be recorded in the eCRF. A computer-generated randomization list will be created using SAS

CONFIDENTIAL 31 (59)

Proc Plan, SAS Version 9.4 or later (SAS Institute, Inc., Cary, NC). The randomization list will contain subject number, IP administration sequence, period, and IP.

The randomization list will be generated by CTC and a copy of the randomization list will be provided to the packing company and to the clinic. The original randomization list will be kept by the randomizer.

Because this is an open-label study, no blinding procedures will be followed.

CONFIDENTIAL 32 (59)

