11.3 Assessments related to primary endpoints

11.3.1 Nicotine plasma concentration and pharmacokinetic sampling

Venous blood samples (approximately 3 mL) for the determination of plasma concentrations of nicotine after IP administration will be collected through an indwelling venous catheter at pre-defined time-points; pre-administration (within 15 min prior to dose), and 5 min, 10 min, 15 min, 30 min, 45 min, 60 min, 1 h:15 min, 1 h:30 min, 2 h, 4 h, and 6 h post-administration, see Table 8.1-2. It is important that blood PK sampling does not deviate from the planned time more than the allowed time deviations outlined in Table 11.1-1.

The date and time of collection of each sample will be recorded in the eCRF.

The blood samples will be collected in pre-labelled tubes. All the collected blood samples will be centrifuged to separate plasma. The separated plasma from each blood sample will be divided into 2 aliquots in pre-labelled cryotubes and frozen at -20°C.

For further details see the lab manual.

Plasma samples for determination of plasma concentrations of nicotine will be analyzed by Lablytica by means of a validated liquid chromatography-tandem mass spectrometry (LC-MS/MS) method.

CONFIDENTIAL 37 (59)

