17 STATISTICAL METHODS AND DETERMINATION OF SAMPLE SIZE

The principal features of the statistical analysis to be performed are described in this section. A more technical and detailed elaboration of the principal features will be presented in a separate Statistical Analysis Plan (SAP), which will be signed and approved prior to database lock.

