17.3 Pharmacokinetic analysis

The PK analysis will be based on the pharmacokinetic analysis set (PKAS) and performed by CTC. The PK parameters will be calculated by NCA using the software Phoenix WinNonlin® version 8.1 or later (Certara Inc, Princeton, New Jersey, U.S.A.). In addition to AUC_{inf} and terminal elimination half-life ($T_{1/2}$) parameters, other non-compartmental PK parameters will be determined in relation to secondary endpoints (see Section 17.7.2 below). Where possible, both baseline-adjusted and non-adjusted PK parameters will be calculated.

For AUC_{inf} , the area under the plasma concentration vs. time curve will be calculated to the time point of the last quantifiable plasma concentration of nicotine and then extrapolated to infinity using the concentration in the last quantifiable sample and the estimated terminal elimination rate constant (Lambda_z).

PK data will be presented for each IP using summary statistics. This data will be presented in terms of N, arithmetic mean, SD, minimum and maximum value. For AUC and C_{max}

CONFIDENTIAL 53 (59)

parameters, the geometric mean and CV will be presented. Categorical data will be presented as counts and percentages as applicable.

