17.4.2 PK analysis set

The PK analysis set (PKAS) will consist of all subjects who received at least 1 IP administration and provided at least 1 evaluable PK-profile and no major deviation judged to compromise the PK analysis. Individual PK values and/or full profiles for explicit IPs may be excluded from the analysis as specified in the SAP.

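### Section 8.2 gives the randomization list to the bioanalytical laboratory and the pharmacokineticist, who do not need product identity; this is an avoidable, unquantified risk of bias in the primary AUCinf.

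*Protocol*

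**What the plan says.** Protocol section 8.2 closes with: "A copy of the randomization list will be generated and provided to the bioanalytical laboratory and to the pharmacokineticist for their analyses". Section 9.9 says that the list will "contain subject number, IP administration sequence, period, and IP", so whoever holds it can tell which product lies behind each sample and profile. Section 9.9 also names recipients: "a copy of the randomization list will be provided to the packing company and to the clinic". It adds: "Because this is an open-label study, no blinding procedures will be followed".

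Plasma nicotine is measured "by means of a validated liquid chromatography-tandem mass spectrometry (LC-MS/MS) method" (section 11.3.1). On parameter derivation, section 17.3 says: "The PK analysis will be based on the pharmacokinetic analysis set (PKAS) and performed by CTC". CTC is also the organisation that generates the list (section 9.9). AUCinf is extrapolated beyond the last quantifiable sample with an estimated Lambda_z (section 17.3).

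Membership of the PK analysis set requires "no major deviation judged to compromise the PK analysis" (section 17.4.2). The same section lets single values or entire profiles for a given product be dropped under rules that the SAP is to set. Section 17 describes the SAP as a document "which will be signed and approved prior to database lock", and section 16.7 places the analysis after that lock. No section masks the laboratory or the pharmacokineticist, or says when they receive the list.

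**The concern.** Subjects using flavored and unflavored pouches cannot be blinded, and the study does not try to blind them. The people who produce concentrations and derive AUCinf are in a different position: they could work without knowing the product, and section 8.2 tells them which it is.

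The primary conclusion is whether the 90% confidence interval for a ratio of AUCinf lies within 0.8-1.25 (section 17.6.1). Deriving AUCinf can involve judgment at two points: which points define the terminal slope, and which values or profiles are flagged as unusable. If such choices are made with the product known, even without intent, they can move the ratio in one direction, and the data would not show afterwards that this had happened. Section 6.1 says that the results are meant to support a premarket application to the FDA, where an unmasked derivation of the primary parameter is an easy ground for doubt.

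**Working it through.** **1. Does either recipient need the product?**
- Laboratory: section 10.1 lists nine products, each with 6 mg nicotine, and section 11.3.1 names nicotine as the substance measured. No placebo is described whose samples could be skipped. Subject, visit and time point identify every sample.
- Pharmacokineticist: sections 17.3 and 17.7.2 derive AUC, Cmax, Tmax and half-life from the concentrations and actual sampling times of one profile. The product enters only when results are tabulated and compared.
- Section 8.2 gives no reason beyond the recipients' own analyses.

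**2. What discretion does the protocol already remove?** Section 17.7.2 fixes the handling of values below the quantification limit, the use of actual times and the interpolation method. The protocol leaves open the choice of Lambda_z points and the reading of a compromising deviation. The SAP, which is not at hand, may fix both.

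**3. How much of AUCinf depends on Lambda_z?** The last sample is at 6 h and the pouch is held for 1 h. The protocol gives no half-life, so 2 to 3 h is an assumption. For a one-compartment model with constant input over 1 h, ignoring baseline nicotine, and with k = ln 2 / half-life:

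fraction of AUC beyond 6 h = ((e^k − 1)/k) × e^(−6k)

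- 2 h: k = 0.347; 1.195 × 0.125 = 14.9%
- 2.5 h: k = 0.277; 1.152 × 0.189 = 21.8%
- 3 h: k = 0.231; 1.125 × 0.250 = 28.1%

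The extrapolated area varies as 1/Lambda_z. If Lambda_z were 10% lower for one product (an arbitrary figure), that area would grow by 1/0.9 − 1 = 11.1%, and AUCinf by 0.149 × 0.111 = 1.7%, 0.218 × 0.111 = 2.4%, or 0.281 × 0.111 = 3.1%.

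**4. What would a shift of that order do to the equivalence test?** The inputs from section 17.2 are CV 32.5%, 36 evaluable subjects, limits 0.8-1.25 and no true difference.
- σ = √ln(1 + 0.325²) = 0.3169; standard error = 0.3169 × √(2/36) = 0.0747.
- Two one-sided tests at 5% each, with 34 degrees of freedom, give 80.0% power. The plan's figure is reproduced.
- With a true ratio of exactly 0.80, the chance of wrongly declaring equivalence is 5.0%. If the estimate is moved toward 1 by an assumed 1%, 2%, 3% or 5%, it becomes 6.5%, 8.3%, 10.4% or 15.7%.

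Steps 3 and 4 show sensitivity to assumed shifts. Nothing in the protocol indicates that any such shift would occur.

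**The case against.** The strongest reply is that the study is declared open-label and states that it uses no blinding procedures. Section 8.2 is therefore a disclosed choice, consistent with the rest of the protocol. That stands: this is not an error or a contradiction. It does not show that the laboratory or the pharmacokineticist needs the list.

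Second, if the SAP fixes the Lambda_z and exclusion rules, little is left to judgment. That also stands. The SAP is to be signed before lock and the analysis follows the lock, so the absence of these rules from the protocol is no finding.

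Third, the assay is validated and objective. Moving AUCinf by 2-3% would take a systematic slope shift in one product across subjects, and that is small against limits of 0.8-1.25. This is fair, and it is why no size of bias is claimed.

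Stronger readings are tempting but are not supported:
- A reader might infer that sample reruns are decided with the product known. The protocol never mentions reruns.
- A reader might infer that exclusions are certainly made by people holding the list. The protocol says neither who decides them nor when the list is released.
- A reader might see sections 8.2 and 9.9 as contradictory because they name different recipients. Section 9.9 does not say that its recipients are the only ones, so aligning the two is editorial.
- A reader might say that the SAP is signed too late. Signing it before concentrations are released would be stricter practice, but the stated order is not wrong.

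**Conclusion.** The point holds as a cheap improvement to the design. Section 8.2 gives product identity to two parties who can do their work without it, and no step requires their choices to be locked first. Judgments on Lambda_z, flagged values or profiles may therefore be made with the product known.

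The size of any resulting bias cannot be derived from the protocol. The 1.7-3.1% change in AUCinf rests on an assumed half-life of 2 to 3 h and an arbitrary 10% slope shift confined to one product. The false-equivalence rates rest on assumed shifts and a true ratio at the limit. The risk shrinks to the extent that the SAP fixes the slope and exclusion rules.

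**What to change.** In section 8.2, delete the bioanalytical laboratory as a recipient and identify its samples by subject, visit and time point. Give the pharmacokineticist profiles coded by subject and visit. Release product codes only after Lambda_z choices, flagged values and PK analysis set exclusions have been documented and locked.

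Editing section 8.2 alone will not mask the pharmacokineticist, because CTC both generates the list and performs the PK analysis. An access restriction within CTC is needed as well. While editing, bring the recipients named in sections 8.2 and 9.9 into line.

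The cost is a revised sentence, a data-transfer instruction, a small coding and access step, and one short extra lock before the product-level PK tables. Sample size, visits and the statistical model do not change.

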9 STUDY POPULATION

Prospective approvals of protocol deviations from eligibility criteria, also known as protocol waivers or exemptions, are not permitted.

9.1 Recruitment

The subjects will be recruited from CTC's database of healthy volunteers, as well as from strategic marketing campaigns. Advertisements in social media and other media (newspapers, internet, radio, local distribution of flyers et c.) will be used to reach the target audience. The advertisement texts approved by the independent ethics committee (IEC) will be used to create all the materials (digital, radio and/or print) for recruitment.

9.2 Screening and enrolment log

The PI must keep a record of all screened subjects even if they were not subsequently included in the study. This information is necessary to verify that subjects were selected without bias. The reason for screen failure should be stated for all subjects that were screened but not included. The reason for withdrawal should be stated for all subjects that were included but did not complete the study.

A screening number will be allocated to each subject in connection to the informed consent process at the screening visit (Visit 1). The screening number is generated automatically in the electronic case report form (eCRF). The screening number will allow identification of subjects irrespective of their possible eligibility for the study.

Subjects included and randomized will be assigned a randomization number (101, 102 et c.).

If a subject cannot receive the planned dose of IP within 28 days after screening (*i.e.*, the time interval between signing informed consent until dose administration) the subject should be re-screened before proceeding in the study.

9.3 Number of subjects

Forty-two (42) subjects will be included in the study. Approximately 63 subjects will be screened with the aim to achieve 42 randomized subjects and 36 fully evaluable subjects. A fully evaluable subject is defined as a subject who has received all 9 IPs and who has completed all study visits. An effort will be made to randomize at least 17 female subjects (~40 %), however a minimum of 9 randomized female subjects (~20 %) will be considered acceptable.

For replacements of subjects who discontinue from the study, see Section 9.8.3.

9.4 Inclusion criteria

To be included in the study, subjects must fulfil the following criteria:

- 1. Willing and able to give written informed consent for participation in the study.
- 2. Subjects who have used oral tobacco/nicotine products for ≥ 1 year, with a minimum daily consumption of 5 or more pouches, and who are willing and able to use products with nicotine content ≥ 1 %
- 3. Healthy male or female subject aged ≥ 21 years.

CONFIDENTIAL 28 (59)

- 4. Clinically normal medical history, physical findings, vital signs, ECG, and laboratory values at the time of screening, as judged by the Investigator.
- 5. Female subjects of child-bearing potential must be willing to use a sufficient contraceptive method for the duration of the study, this includes mechanical barrier (*e.g.*, a male condom or a female diaphragm), combined [estrogen and progestogen containing] hormonal contraception associated with inhibition of ovulation [oral, intravaginal, transdermal], progestogen-only hormonal anticonception associated with inhibition of ovulation [oral, injectable, implantable], intra uterine device (IUD) or intra uterine system (IUS). Sexual abstinence is allowed when this is the preferred and usual lifestyle of the subject.

9.5 Exclusion criteria

Subjects must be excluded from the study if any of the following exclusion criteria are fulfilled:

- 1. A history of diagnosed hypertension or any cardiovascular disease, or ongoing manifestations of hypertension or any cardiovascular disease as judged by the Investigator.
- 2. Any surgical or medical condition, including abnormal salivation (also pharmaceutically induced), or history thereof, which, in the judgment of the Investigator, might interfere with the absorption, distribution, metabolism or excretion of the IP or may either put the subject at risk because of participation in the study, influence the results, or the subject's ability to participate in the study.
- 3. Subjects who are pregnant, breastfeeding, or intend to become pregnant during the course of the study.
- 4. Any positive result on screening for serum hepatitis B surface antigen, hepatitis C antibody and Human Immunodeficiency Virus (HIV).
- 5. A history of diagnosed severe allergy/hypersensitivity or ongoing manifestations of severe allergy/hypersensitivity to aroma compounds (including fragrances and/or flavorings), as judged by the Investigator.
- 6. Positive screen for drugs of abuse or alcohol at screening or on admission to the unit prior to first IP administration. Positive results that are expected given the subject's medical history and prescribed medications can be disregarded as judged by the Investigator.
- 7. Current, ongoing use of beta-adrenergic blocking agents (beta blockers), including *pro re nata* (as needed) use.
- 8. Current or history of alcohol abuse and/or use of anabolic steroids or drugs of abuse, as judged by the Investigator.
- 9. Plasma donation within 1 month of screening or blood donation (or corresponding blood loss) during the 3 months prior to screening.
- 10. Subjects who intend to change their nicotine consumption habit, including the intention to stop using nicotine products, within the next 3 months from the screening visit, as judged by the Investigator.
- 11. The Investigator considers the subject unlikely to comply with study procedures, restrictions, and requirements.

CONFIDENTIAL 29 (59)

